8.3.1.3 Follow-up MRI Imaging Visits

Patients must receive the required MRI scans at one, two and five years after enrolment. Scans should be obtained within a window of -1 month- 2+ months around these data collection time points. If the MRI is not performed within the specified time frame (-1 month-2+ months of the estimated date for the one, two and five year MRIs), then the SCC will notify the regional study site and this will be documented as a protocol deviation. Regional study site staff will assist the patient in scheduling an appointment for the MRI imaging.

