8. RESEARCH METHODS

8.1 Study Design

This is a multi-centre long-term open-label non-comparative study to assess changes in carotid and aortic atherosclerosis in patients being treated with lomitapide. Patients from the European Union (EU), the United States (US) and Canada who are being treated with lomitapide and are enrolled in LOWER will be invited by the LOWER enrolling physician to participate in this substudy. Each LOWER enrolling physician will be instructed to invite consecutive patients who meet the eligibility criteria. Sites will be asked to keep a log of the patients invited identified only by Identification (ID) number, indicating those who declined participation or did not meet eligibility criteria. Patients who agree to participate will be referred to a regional site to further assess eligibility.

The regional study sites selected will have the resources to perform all study related procedures including patient screening and enrolment, MRI imaging, blood draws and processing, patient follow-up, and data storage and transfer. These sites will be selected on a regional basis and may include some sites that are also enrolled in LOWER.

After the regional site confirms patient eligibility and the patient provides informed consent for the vascular sub-study, the patient will be scheduled to have a baseline integrated vascular MRI assessment as well as laboratory assessments. If the patient is already being treated with lomitapide, a baseline MRI must occur within three months of initiating treatment. Additional MRI assessments will be performed at years one, two and five after enrolment. All MRI images will be sent to a central Imaging Core Laboratory for qualitative and quantitative image analysis.

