8.2.1.1 Inclusion Criteria

- Adult patients (age ≥ 18 years) who are enrolled in LOWER
- Patients who:
 - Are initiating treatment with lomitapide at the time of enrolment in this study,
 - or
 - Have initiated treatment with lomitapide within 3 months prior to enrolment in this study
- Patients who have the ability to understand the requirements of the study, and provide written informed consent to comply with the requirements for periodic MRI assessments.

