8.3.1.2 Baseline MRI Scan

In order to be eligible for this study, a patient must have his/her baseline MRI scan within three months after initiating therapy with lomitapide. The baseline MRI should ideally be scheduled as soon as possible after enrolment and prior to initiation of lomitapide therapy.

Patients must have a baseline MRI scan that is deemed evaluable with an acceptable image quality of carotid arteries (both left and right carotid arteries) and aorta as determined by the central Imaging Core Laboratory in order to proceed to the follow up visits. All MRI scans must be immediately sent to the central Imaging Core Laboratory for qualitative image analysis. The central Imaging Core Laboratory will provide a rapid turnaround (within one week) of the image quality evaluation. The image quality evaluation will be sent to the regional study site as well as to the SCC so that, in the event that a repeat MRI is required, the site can contact the patient to return for additional scans.

Each regional study site will provide data to the central Imaging Core Laboratory following the guidelines set forth in the MRI Imaging Facility Charter ([Section 8.3.2](#)). The central Imaging Core Laboratory will notify the regional study site and the SCC that the MRI is acceptable, or if a repeat MRI is required. The SCC will request that the regional study site Investigator or his/her designee either complete the notification form if the testing was completed or contact the patient and schedule a repeat MRI. An MRI image deemed acceptable by the central Imaging Core Laboratory must be confirmed within three months of the patient starting lomitapide treatment. If delays result in the imaging being done outside of the three month window since starting lomitapide treatment, the patient will not be eligible to continue in the study.

The central Imaging Core Laboratory will transfer analysed results to SCC in a pre-specified format and time-frame as specified in the DMP.

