8.5.1 Efficacy Endpoints

The primary objective of the study is to assess the change in carotid atheroma as reflected by carotid vessel wall area on MRI scanning following two years of treatment with lomitapide. The endpoint used to address this objective will be the percent change in carotid vessel wall area from baseline to two years on lomitapide therapy, where percent change is calculated as $100 * \{WA(24) - WA(0)\} / WA(0)$. WA(x) denotes wall area at either baseline (x=0) or 24 months (x=24). The mean area obtained from the left and right carotid arteries will be used in the primary analysis; additional analyses will consist of individual results from the left and right arteries separately. Refer to Section 8.5.2 for the derivation of wall area measurements.

The secondary objectives of the study are:

- To assess the changes in atheroma burden as reflected by changes in average aortic vessel wall area, average aortic and carotid vessel lumen area, total vessel area, wall thickness, normalized wall index and standard deviation of wall thickness on MRI following two years of lomitapide treatment compared to baseline.

- To assess the changes in atheroma burden as reflected by changes in average aortic and carotid vessel wall area, lumen area, total vessel area, wall thickness, normalized wall index and standard deviation of wall thickness following one year and five years of lomitapide treatment compared to baseline.
- To assess changes in LDL-C and other lipoproteins at one, two and five years of lomitapide treatment compared to baseline and the correlation of these laboratory evaluations with the change from baseline in MRI parameters of carotid and aortic atheroma.

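### Follow-up scans are timed from enrolment, not from the accepted baseline scan, so an in-window two-year scan can fall only about 20 months after baseline

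*Protocol*

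**What the plan says.** The protocol uses three time origins for one within-patient change.

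- **Follow-up schedule: enrolment.** Section 8.3.1.3 states "Patients must receive the required MRI scans at one, two and five years after enrolment". Section 8.1 agrees: "Additional MRI assessments will be performed at years one, two and five after enrolment". Section 3.4 says the same, and 8.3.1.4 ties the blood draws to the same dates. The tolerance is "Scans should be obtained within a window of -1 month- 2+ months around these data collection time points".
- **Baseline scan: first dose.** Section 8.3.1.2 requires that "a patient must have his/her baseline MRI scan within three months after initiating therapy with lomitapide". It provides for recall and repeat scanning if the core laboratory rejects an image, subject to this limit: "An MRI image deemed acceptable by the central Imaging Core Laboratory must be confirmed within three months of the patient starting lomitapide treatment".
- **Endpoint: baseline scan and time on treatment.** Section 8.5.1 defines the primary endpoint as the "percent change in carotid vessel wall area from baseline to two years on lomitapide therapy", and its formula labels the two measurements month 0 and month 24. Section 8.4 powers the study on the change from baseline to 24 months.

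On drug start relative to enrolment, 8.2.1.1 admits new starters through the criterion "Are initiating treatment with lomitapide at the time of enrolment in this study". A second, alternative criterion covers those already taking the drug: "Have initiated treatment with lomitapide within 3 months prior to enrolment in this study".

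**The concern.** The follow-up clock starts at enrolment, while the endpoint is measured from the accepted baseline scan. If the first scan is rejected or scheduled late, the accepted baseline moves later and the follow-up date does not. The interval shrinks, and no deviation is recorded.

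This matters because the study is uncontrolled. Section 8.9.1 says the within-patient estimate will have to be compared with historical or literature results, and such a comparison needs a known interval. A late baseline also acts in one direction only: it can shorten the interval relative to the schedule but never lengthen it. The one-year change in wall area and wall thickness, a key secondary endpoint in 8.5.4.3, is affected proportionally more.

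**Working it through.** **The plan's own figure.** Section 8.4 gives SD 22%, a 10% change, two-sided 0.05, 80% power and 40 evaluable patients. A one-sample t-test (noncentral t) gives n = 40 with power 0.8005; the normal approximation gives 37.99, i.e. 38. For enrolment, 40/(1 − 0.30) = 57.1, matching the stated 57. The sample size reproduces, and it assumes a 24-month change.

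**Inputs for the interval**, in months with enrolment = 0:

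- drug start s between −3 and 0 (8.2.1.1)
- accepted baseline scan b between 0 and s + 3 (8.3.1.2)
- two-year scan f between 24 − 1 = 23 and 24 + 2 = 26 (8.3.1.3)

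**Scan-to-scan interval = f − b.**

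- Shortest: s = 0, b = 3, f = 23, so 23 − 3 = 20. The image must be confirmed, not merely taken, within three months. If the one-week read is used in full (7/30.44 = 0.23 month), the shortest is 23 − (3 − 0.23) = 20.2.
- Longest: b = 0, f = 26, so 26.
- Baseline done at enrolment (b = 0): 23 to 26.
- A patient already on drug has less room for a late baseline. With s = −3, b must be 0 and the interval is again 23 to 26.
- Year one by the same rule: 11 − 3 = 8 to 14 − 0 = 14. Year five: 59 − 3 = 56 to 62.

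**Time on drug at the two-year scan = f − s.** The range is 23 − 0 = 23 to 26 + 3 = 29.

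**Same limits, with follow-up timed from b.** The interval becomes 23 to 26 at year two, 11 to 14 at year one and 59 to 62 at year five. Time on drug at year two is (b − s) + 23 to 26. Since b − s runs from 0 to 3, it stays at 23 to 29.

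**Size, assuming change is linear in time** (the protocol does not state this):

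- A 10% change over 24 months reads as 10 × 20/24 = 8.3% at 20 months. A one-year change read at 8 months is 8/12 = 67% of its 12-month value.
- A full three-month delay costs a patient 10 × 3/24 = 1.25 percentage points. If one patient in five were so delayed (illustrative), the mean would move by 0.25 points.
- Intervals spread evenly over 20 to 26 months have SD 6/√12 = 1.73 months, or 10/24 × 1.73 = 0.72 percentage points. The outcome SD becomes √(22² + 0.72²) = 22.01.
- That spread has a mean of 23 months, an expected change of 9.6% and power of about 77% at n = 40. Power falls to about 65% only if every patient had a 20-month interval.

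**The case against.** The strongest reply is that the protocol intends the baseline scan at enrolment. Section 3.4 has it done at once on enrolment, 8.3.1.1 lists it among the enrolment-visit items, and 8.3.1.2 asks for it early, with a quality read within a week. For a patient handled that way, the interval is 23 to 26 months under either anchor. This stands: 20 months is a permitted extreme, not a typical case. It does not remove the point. Section 8.1 says only that the scan will be scheduled, and 8.3.1.2 expressly plans for rejected and repeated baselines, while 8.3.1.3 makes no allowance for them.

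Three stronger readings are tempting, and the protocol does not support them.

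- A reader might blame the enrolment anchor for the 23 to 29 months on drug. That range comes from the three-month entry allowance plus the visit window, and re-timing leaves it unchanged. The 26-month upper end of the scan interval likewise comes from the window alone.
- A reader might infer that the primary analysis is materially underpowered or biased towards regression. Under linear change a short interval shrinks the change in either direction, and the loss is small unless late baselines are frequent.
- A reader might infer intervals well below 20 months, because 8.3.1.2 foresees a scan before first dose and sets no explicit limit on how long after enrolment dosing may start. The inclusion criterion ties dosing to enrolment, though loosely, so I do not rely on this.

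It can also be said that adjustment for interval belongs in the SAP, which was not available to me. That is fair for the analysis. It does not cover the visit dates, which the protocol fixes and which no later analysis plan can move.

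**Conclusion.** The point holds in limited form. The follow-up schedule and the primary endpoint have different origins, and the baseline rules allow the gap between them to reach about three months. Without any deviation, a two-year scan can fall about 20 months after baseline and a one-year scan about 8 months after. The part due to the enrolment anchor is the stretch from 20 to 23 months at year two and from 8 to 11 at year one.

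The reading of 8.3% for a true 10% rests on linear change and on the extreme case. How often late baselines would occur cannot be derived from the protocol. The likely effect on the primary result is modest. The change is worth making because the shortening runs in one direction in an uncontrolled before-after study and is easy to prevent.

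**What to change.** In 3.4, 8.1, 8.3.1.3 and 8.3.1.4, time the one-, two- and five-year scans and blood draws from the date of the accepted baseline MRI, keeping the existing window. In 8.5.1, state that month 24 is counted from that scan, and reconcile this with the wording there about two years on therapy.

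Optionally, add a supportive analysis of the primary endpoint that adjusts for the scan-to-scan interval and for months on lomitapide, taken from the LOWER exposure data that are already transferred. Only this second step addresses the 23 to 29 months on drug.

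The cost is a wording change and a new reminder date at the coordinating centre, which already receives the core laboratory's notice that a baseline image is acceptable. No scans are added. Visits move by up to three months for patients with late baselines.

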8.3.1.4 Patient Follow-up for Laboratory Assessments

Blood for the laboratory assessments required for this study should be collected by the regional study site at the time of the patient's MRI scan at one, two, and five years after enrolment in the study (-1 month-2+months). Blood will be processed as described in a separate laboratory manual and will be sent to the Central Laboratory for analysis.

The specific laboratory assessments for lipoprotein, inflammatory and cardiovascular biomarkers are:

Lipoprotein biomarkers

- Total cholesterol (TC)
- High density lipoprotein (HDL-C)
- Low density lipoprotein (LDL-C)
- Triglycerides (TG)
- Apolipoprotein B (apo B)
- Apolipoprotein A-I (apo AI)
- Lipoprotein (a) (Lp(a))
- Apolipoprotein C-III (Apo C-III)
- LDL sub-fractions using NMR technology

Inflammatory and cardiovascular biomarkers

- High sensitivity C reactive protein (hs-CRP)
- Serum amyloid A (SAA)

- Soluble Inter-cellular Adhesion Molecule-1 (sICAM-1)
- Interleukin 6 (IL-6)
- Lipoprotein Associated Phospholipase 2 (LpPLA2)
- Soluble Vascular Cell Adhesion Protein 1 (sVCAM-1)
- Soluble E-selectin (sE-selectin)
- Soluble interleukin-6 receptor (sIL-6 Receptor)
- Fasting glucose and insulin and calculate HOMA (Homeostasis Model Assessment)

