7. RESEARCH QUESTION AND OBJECTIVES

The study is designed to evaluate the effects of lomitapide on carotid and aortic atherosclerosis in patients treated in clinical practice by collecting direct evidence of the antiatherosclerotic effect of lomitapide on vessel wall morphology.

The primary objective of this study is:

- To assess the changes in atheroma burden as reflected by average carotid vessel wall area on MRI scanning following two years of treatment with lomitapide compared to baseline.

Secondary objectives of this study are:

- To assess the change in atheroma burden as reflected by changes in average aortic vessel wall area, average aortic and carotid vessel lumen area, total vessel area, wall thickness, normalized wall index and standard deviation of wall thickness on MRI following two years of lomitapide treatment compared to baseline.
- To assess the change in atheroma burden as reflected by changes in average aortic and carotid vessel wall area, lumen area, total vessel area, wall thickness, normalized wall index and standard deviation of wall thickness following one year and five years of lomitapide treatment compared to baseline.
- To assess changes in LDL-C and other lipoproteins at one, two and five years of lomitapide treatment compared to baseline and the correlation of these laboratory evaluations with the change from baseline in MRI parameters of carotid and aortic atheroma.

Exploratory analyses of this study are:

- To evaluate major plaque compositional features including the necrotic lipid area, fibrous cap thickness and calcium area. These plaque composition analyses will be performed at imaging time points if sufficient data exist with respect to both the size and frequency of the plaques.

- To assess changes in markers of inflammatory and cardiovascular processes at one, two, and five years of lomitapide treatment compared to baseline, and to correlate these changes with the change from baseline in MRI parameters of carotid and aortic atheroma.

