8.3 Variables

8.3.1 Patient Data Collection

For patients enrolled in this substudy, all of their relevant individual data collected in LOWER will be included in the study database. The relevant data points will be transferred into the study database as described in a separate data management plan (DMP). Therefore, patient demographic data, medical history, and lomitapide exposure data will not be necessary to collect again in this study. A Central Laboratory will be used for this study.

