8.3.1.1 Regional Study Site Enrolment Visit

At the LOWER enrolment visit, after the patient has provided written consent to participate in LOWER, the LOWER enrolling physician (or designee) will provide an overview of this vascular imaging study to each patient. The LOWER enrolling physician will notify the SCC of interested patients. The SCC will then notify the regional study

site. The regional study site will contact the patient to assess eligibility and obtain informed consent. For patients who are not located near the regional site, verbal informed consent will be obtained first by phone with written informed consent obtained at the baseline visit, prior to any procedures being performed. Enrolled patients will have a baseline MRI scan at the regional study site prior to initiating lomitapide therapy or within three months after initiating lomitapide therapy.

The following will be collected at the enrolment visit:

- Date of written informed consent
- Confirmation of eligibility criteria
- Laboratory tests (lipoprotein, inflammatory and cardiovascular biomarkers)
 - Lipoprotein biomarkers
 - Total cholesterol (TC)
 - High density lipoprotein (HDL-C)
 - Low density lipoprotein (LDL-C)
 - Triglycerides (TG)
 - Apolipoprotein B (apo B)
 - Apolipoprotein A-I (apo AI)
 - Lipoprotein (a) (Lp(a))
 - Apolipoprotein C-III (Apo C-III)
 - LDL sub-fractions using nuclear magnetic resonance (NMR) technology
 - Inflammatory and cardiovascular biomarkers
 - High sensitivity C reactive protein (hs-CRP)
 - Serum amyloid A (SAA)
 - Soluble Inter-cellular Adhesion Molecule-1 (sICAM-1)
 - Interleukin 6 (IL-6)
 - Lipoprotein Associated Phospholipase 2 (LpPLA2)
 - Soluble Vascular Cell Adhesion Protein 1 (sVCAM-1)
 - Soluble E-selectin (sE-selectin)

- Fasting glucose and insulin and calculate HOMA (Homeostasis Model Assessment)
- Baseline MRI

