8.5.4.4 Exploratory Endpoint Analysis

The analysis of exploratory endpoints will be descriptive only. Exploratory endpoints will consist of lumen area, total vessel area, standard deviation of wall thickness and the normalized wall index, at baseline, one, two, five years and one year post discontinuation of lomitapide if available. Exploratory endpoints will also include laboratory evaluations of biomarkers for inflammatory and cardiovascular processes. Correlation analysis will be performed between changes in these potential biomarkers and the change from baseline in MRI parameters of carotid and aortic atheroma.

The major plaque compositional features will include the necrotic lipid area, fibrous cap thickness and calcium area. These are quantified as either present or absent by subjective analysis, and will be analysed as categorical data through summary statistics of number and percentage of positive and negative results. These plaque composition analyses will be performed if sufficient data exist with respect to both the size of the plaques as well as frequency.

Inflammatory and cardiovascular biomarkers include:

- High sensitivity C reactive protein (hs-CRP)
- Serum amyloid A (SAA)
- Soluble Inter-cellular Adhesion Molecule-1 (sICAM-1)
- Interleukin 6 (IL-6)
- Lipoprotein Associated Phospholipase 2 (LpPLA2)
- Soluble Vascular Cell Adhesion Protein 1 (sVCAM-1)
- Soluble E-selectin (sE-selectin)
- Soluble interleukin-6 receptor (sIL-6 Receptor)
- Fasting glucose and insulin and calculate HOMA (Homeostasis Model Assessment)

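### Soluble IL-6 receptor is on the follow-up and analysis lists but not on the enrolment list, so its planned change from baseline cannot be computed

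*Protocol*

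**What the plan says.** The protocol itemises the inflammatory and cardiovascular biomarkers in three places.

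- **Section 8.3.1.1 (enrolment visit).** The list is introduced by "The following will be collected at the enrolment visit" and, under "Laboratory tests (lipoprotein, inflammatory and cardiovascular biomarkers)", names each analyte. Its last two biomarker entries are "Soluble E-selectin (sE-selectin)" and then fasting glucose and insulin with HOMA.
- **Section 8.3.1.4 (follow-up).** Blood is taken at the time of the patient's "MRI scan at one, two, and five years after enrolment in the study". This list has "Soluble interleukin-6 receptor (sIL-6 Receptor)" between soluble E-selectin and glucose/insulin/HOMA.
- **Section 8.5.4.4 (exploratory analysis).** The list has the same entries as the follow-up list, including soluble IL-6 receptor. It also says that "Correlation analysis will be performed between changes in these potential biomarkers" and the MRI changes from baseline.

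The exploratory objective in section 7, repeated in section 3.3, is "To assess changes in markers of inflammatory and cardiovascular processes at one, two, and five years of lomitapide treatment compared to baseline", and to correlate those changes with the MRI changes.

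**The concern.** A change from baseline needs a baseline value. The protocol schedules soluble IL-6 receptor at every follow-up time point and lists it for analysis, but not at the one visit that would supply the reference value.

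The gap is time-critical. Baseline here means before lomitapide or within three months of starting it. Once that window has closed, a new sample cannot stand in for the missing one. Nothing written later, including a statistical analysis plan, can supply a value that was never measured.

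**Working it through.** No sample size, power or error rate is involved, so the check is an entry-by-entry comparison of the lists.

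| Inflammatory / cardiovascular entry | Enrolment (8.3.1.1) | Years 1, 2, 5 (8.3.1.4) | Analysis (8.5.4.4) |
|---|---|---|---|
| hs-CRP | yes | yes | yes |
| Serum amyloid A | yes | yes | yes |
| sICAM-1 | yes | yes | yes |
| IL-6 | yes | yes | yes |
| LpPLA2 | yes | yes | yes |
| sVCAM-1 | yes | yes | yes |
| sE-selectin | yes | yes | yes |
| **sIL-6 receptor** | **no** | **yes** | **yes** |
| Glucose, insulin, HOMA | yes | yes | yes |
| **Total entries** | **8** | **9** | **9** |

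Soluble IL-6 receptor is the only difference. As a control, the lipoprotein lists in sections 8.3.1.1, 8.3.1.4 and 8.5.4.3 were compared in the same way: each has nine entries and they match. The marker is also in the list of abbreviations (section 1), so it is an intended measurement and not a stray entry.

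**What can be computed for this marker as written**

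- Baseline values per patient: 0.
- Follow-up values per patient: up to 3 (years one, two and five).
- Changes from baseline: 0 of the 3 planned.
- Correlations of those changes with MRI change: none.
- Differences between follow-up visits, such as year one to year two, remain possible but are not the stated objective.

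**Follow-up assays affected.** With the 57 patients of section 8.4 and three follow-up visits each, 3 × 57 = 171. This assumes that all 57 are followed to year five. Section 8.4 itself expects 15% dropout over two years, which would lower the count, and sets 57 as a minimum enrolment, so the figure is illustrative.

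**Other possible sources of a baseline value.** Section 8.3.1 says that "all of their relevant individual data collected in LOWER will be included in the study database", but the examples it gives are demographics, medical history and lomitapide exposure. Nothing states that LOWER measures soluble IL-6 receptor. Section 8.3.1.4 cites a separate laboratory manual for how blood is processed, while the protocol itself lists the assays.

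**The case against.** The strongest points on the other side are these.

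- **A line may have been lost in text extraction.** The gap in section 8.3.1.1 falls at an apparent page break, exactly where the entry would stand. A glance at the original page is sensible. However, there is no fragment of a missing line, and a similar break inside the follow-up list lost nothing.
- **The central laboratory may run the full panel on baseline samples anyway.** The enrolment heading uses the same broad categories as the follow-up section, and the laboratory manual is not available here. That is possible, but the protocol does not say it. Section 8.8 bars departures from the protocol without sponsor agreement and documented ethics approval, so the written list is what governs.
- **Loss of the sample is not established.** The protocol is silent on sample volume and storage. It therefore supports neither the view that baseline blood will be used up nor the view that stored serum exists. This stands: retrospective assay depends on what was kept.
- **The weight is small.** Section 8.5.4.4 makes the exploratory analysis descriptive only. IL-6 itself is measured at every visit, and eight of the nine entries are unaffected. This also stands. It limits the consequence but does not remove the contradiction.

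**Conclusion.** The inconsistency is real. Followed as written, the protocol yields no baseline soluble IL-6 receptor value, so its change from baseline and its correlation with MRI change cannot be calculated for any patient at any time point. The loss covers one of nine inflammatory and cardiovascular entries, in an exploratory and descriptive analysis. The primary endpoint, key secondary endpoints, multiplicity procedure, interim analysis and safety analyses do not depend on it.

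It is most likely a drafting slip and not a deliberate choice. It is still worth correcting, because the repair is cheap and the baseline window does not reopen. The conclusion assumes that the enrolment list is complete as printed and that neither LOWER nor the laboratory manual provides the assay at baseline. The protocol gives no sign that either does.

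**What to change.** Make the three lists agree.

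1. **Preferred:** add soluble IL-6 receptor to the enrolment list in section 8.3.1.1, between soluble E-selectin and glucose/insulin/HOMA, and align the laboratory manual. For patients already enrolled without it, state whether baseline samples were stored and, if so, have the marker assayed from them.
2. **If baseline values cannot be obtained:** delete the marker from sections 8.3.1.4 and 8.5.4.4, so that the protocol does not collect follow-up values for an analysis it cannot perform.

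The first option costs one line of text and one extra assay per patient on blood already drawn at enrolment. The second costs two deleted lines and the loss of the marker.
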